9.3.4 Exploratory Endpoint Analyses

The following PK parameters for SUBLOCADE will be derived as shown in Table 8 for BUP and Table 9 for norbuprenorphine using the PK Evaluable Analysis Set. Calculations will be done by noncompartmental analysis using WinNonlin Phoenix. The plasma terminal half-life and AUC extrapolated to infinity (AUC_{0-inf}) are not calculated as the duration of the PK evaluation is shorter than the half-life reported for SUBLOCADE (43-60 days).

Table 8 Additional PK Parameters of BUP Following SUBLOCADE Injection

AUC _{last}	Area under the concentration-time curve from time 0 to the last quantifiable BUP concentration, calculated by the linear trapezoidal method
T _{max}	Time to attain the maximum observed BUP plasma concentration
C _{trough}	Trough BUP plasma concentration measured on Day 29

Confidential 47 of 64

Table 9 PK Parameters of Norbuprenorphine Following SUBLOCADE Injection

AUC _{0-28days}	Area under the concentration-time curve from Study Day 1 to Day 29 of norbuprenorphine, calculated by the linear trapezoidal method
AUC _{last}	Area under the concentration-time curve from time 0 to the last quantifiable concentration of norbuprenorphine, calculated by the linear trapezoidal method
C _{max}	Maximum observed norbuprenorphine plasma concentration
T _{max}	Time to attain the maximum observed norbuprenorphine plasma concentration
C _{trough}	Trough norbuprenorphine plasma concentration measured on Day 29

 AUC_{last} for both analytes, and $AUC_{0-28days}$ and C_{max} for norbuprenorphine will be analysed using the same statistical ANOVA model as described in Section 9.3.2.

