1.1 Synopsis

Protocol Title: A Single-Dose Study to Evaluate the Relative Bioavailability, Safety, and Tolerability of SUBLOCADE at Alternative Injection Locations in Adults

Short Title: SUBLOCADE Alternative Injection Locations

Rationale: SUBLOCADE® (extended-release BUP injection) for SC use (CIII) is currently approved for SC administration in 4 different quadrants of the abdomen. Injection locations are rotated to minimise irritation.

Having 1 or more alternate injection sites is desirable in this patient population who may be taking SUBLOCADE for extended durations, based upon clinical response.

Data cited from literature suggests that the proposed alternative injection locations for SC administration are viable options for delivering similar PK properties: back of upper arm, buttocks, and thigh.

Objectives and Endpoints

Table 1 Objectives and Endpoints

Ok	pjective	Corresponding Endpoint					
Pri	imary						
•	To assess the relative bioavailability of BUP when administered at alternative injection locations (test treatments), in comparison to the abdomen (reference treatment) following a single SC injection of SUBLOCADE in participants with OUD	•	AUC _{0-28days} and C _{max} for BUP				
Se	condary						
•	To evaluate the safety and tolerability of SUBLOCADE when administered at alternative injection locations, in comparison to the abdomen	•	Proportion of participants with TEAEs Proportion of participants with TEAEs identified as injection site reactions Proportion of participants with treatment-emergent SAEs Injection site grading at 10 minutes and 2 hours post SUBLOCADE dosing Injection Site Pain VAS at 1, 5, 10, 15, and 30 minutes post SUBLOCADE dosing				

AUC=area under the curve; BUP=buprenorphine; C_{max} =maximum plasma concentration; OUD=opioid use disorder; SAE=serious adverse event; SC=subcutaneous; TEAE=treatment-emergent adverse event; VAS=visual analogue scale

CONFIDENTIAL 11 of 64

Overall Design Synopsis

This is a multicentre, randomised, open-label, single-dose, parallel-group study in participants with moderate or severe OUD (based on criteria from the DSM-5 or documented history of moderate to severe OUD and receiving/stabilised on MOUD).

Brief Summary: The purpose of this study is to measure the relative bioavailability of BUP when administered at alternative injection locations in comparison to the abdomen following a single SC injection of SUBLOCADE in participants with OUD.

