9.3 Statistical Analyses

9.3.1 General Considerations

Continuous variables will be summarised using descriptive statistics such as mean, SD, median, interquartile range, minimum, and maximum. Categorical variables will be reported as frequency counts (including number missing) and the percentage of participants in corresponding categories.

BUP and norbuprenorphine plasma concentrations following SUBLOCADE injection will be summarised at each scheduled time point by injection location using the PK Analysis set. BUP and norbuprenorphine plasma concentrations during run-in with SUBOXONE film will also be summarised at each scheduled time point using the Enroled participant set for participants who have at least 1 PK sample post SUBOXONE dose. Concentrations that are below the lower limit of quantification (BLQ) will be treated as zero for the summary statistics. Mean BUP and norbuprenorphine plasma concentration-time curves will be presented for the Run-in Period with SUBOXONE film for overall and for SUBLOCADE phase stratified by injection locations.

Details for handling missing and aberrant plasma concentrations for deriving BUP and norbuprenorphine PK parameters will be detailed in the SAP.

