9.3.2.2 Main Analytical Approach

Natural log-transformed $AUC_{0-28days}$ and C_{max} from SUBLOCADE Phase for BUP will be analysed using an ANOVA model with injection site location as the independent variable. The 90% CI will be estimated for the ratio of population geometric means (test/reference) corresponding to exponentiated differences in least square means.

The comparisons of interest are the 3 alternative injection sites (test) versus abdomen (reference, namely: back of upper arm vs abdomen, buttocks vs abdomen, and thigh vs abdomen.)

Confidential 46 of 64

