9.5 Sample Size Determination

No formal statistical power analysis was performed to determine the sample size of this study. Based on historical experience from previous similar clinical trials, approximately 80 randomised participants was considered adequate to achieve at least 15 PK evaluable

Confidential 48 of 64

participants per injection site location to assess the relative bioavailability of SUBLOCADE 300 mg at each of the alternate injection site locations compared to the abdomen (the reference injection location).

Confidential 49 of 64

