STATISTICAL ANALYSIS PLAN: INDV-6000-405

Addendum

Protocol Title: A Single-Dose Study to Evaluate the Relative Bioavailability, Safety, and Tolerability of SUBLOCADE at Alternative Injection Locations in Adults

Final Version: 19 Mar 2024

NCT: NCT05704543

Statistical Analysis Plan Addendum

Protocol ID: INDV-6000-405

[REDACTED]

Date: 19MAR2024

Description:

After database lock, it was noted that the appendix of the SAP the following definition was used to derive medications prior to SUBLOCADE injection.

End Date of Non-Study Medication	Start Date of Non-Study Medication		
	Missing	< Start date of SUBOXONE	≥ Start date of SUBOXONE and ≤ end date of SUBOXONE
Missing (includes flagged as "Ongoing")	Prior Concomitant (Run-In)	Prior Concomitant (Run-In)	Concomitant (Run-In)
< Start date of SUBOXONE	Prior	Prior	Data Error
≥ Start date of SUBOXONE and ≤ end date of SUBOXONE	Prior Concomitant (Run-In)	Prior Concomitant (Run-In)	Concomitant (Run-In)

However, in the last row of this table, it implies that prior medications and Run-In concomitant medications do not include a medication started before injection and ended after last dose of SUBOXONE. The first column last row should not include the clause "and ≤ end date of SUBOXONE".

In addition, medications should be considered run-in concomitant as long as its start date is between start of SUBOXONE and SUBLOCADE injection date (if injection took place). Therefore, the last column should be split into two situations, with and without injection.

After modification, the definition should read the following:

End Date of Non-Study Medication	Start Date of Non-Study Medication			
	Missing	< Start date of SUBOXONE	≥ Start date of SUBOXONE if no injection	≥ Start date of SUBOXONE and ≤ SUBLOCADE injection date if there is SUBLOCADE injection
Missing (includes flagged as "Ongoing")	Prior Concomitant (Run-In)	Prior Concomitant (Run-In)	Concomitant (Run-In)	Concomitant (Run-In)
< Start date of SUBOXONE	Prior	Prior	Data Error	Data Error

≥ Start date of SUBOXONE	Prior Concomitant (Run-In)	Prior Concomitant (Run-In)	Concomitant (Run-In)	Concomitant (Run-In)
--------------------------	----------------------------	----------------------------	----------------------	----------------------

Implications:

Run-In concomitant medications flag and consequently, Table 14.1.5.2 will be updated.

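### Should Day 29 Ctrough have been given a test/abdomen ratio and 90% CI like the other exposure parameters?

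*Protocol*

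**What the plan says.** Section 9.3.2.2 fits a one-way ANOVA with injection location as the factor to log-transformed BUP AUC0-28days and Cmax. It reports test/abdomen geometric mean ratios with 90% CIs for the three alternative sites.

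Section 9.3.4 adds further parameters. Table 8 lists AUClast, Tmax and Ctrough for BUP, with Ctrough defined as "Trough BUP plasma concentration measured on Day 29". Table 9 gives the corresponding Ctrough for norbuprenorphine. The closing sentence sends AUClast for both analytes to the model, together with AUC0-28days and Cmax, which "for norbuprenorphine will be analysed using the same statistical ANOVA model as described in Section 9.3.2". Ctrough and Tmax are not named. The section also explains that half-life and AUC0-inf are not calculated, because follow-up is shorter than the reported half-life of 43-60 days.

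Four other places bear on the point:

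- **Section 3, Table 4** makes Ctrough exploratory for both analytes, under the objectives for other PK parameters.
- **Sections 9.1 and 9.1.1** plan no formal hypothesis and no multiplicity adjustment. Relative bioavailability is judged informally.
- **Section 9.3.1** states that plasma concentrations of both analytes "will be summarised at each scheduled time point by injection location using the PK Analysis set", and plans mean concentration-time curves by location.
- **Section 9, opening paragraph** describes the section as a summary covering the most important endpoints and leaves detail to the SAP.

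**The concern.** The half-life exceeds the sampling period, so AUC0-28days is a partial area. AUClast ends at the same Day 29 sample whenever that sample is quantifiable, so it largely repeats AUC0-28days. Among the derived parameters, only Ctrough looks specifically at late output from the depot, yet it is left out of the model while the near-duplicate AUClast is included.

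If a site both released drug faster and absorbed less in total, the two effects could offset within the first 28 days. AUC0-28days and Cmax would then look similar to abdomen while later exposure was lower. The Day 29 sample is scheduled and the parameter derived, so modelling it appears to cost nothing.

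**Working it through.** **1. Is an analysis missing relative to the objectives?** For norbuprenorphine, Table 4 lists AUC0-28days, AUClast and Cmax under relative bioavailability, and Tmax and Ctrough under other parameters. The three modelled parameters are exactly the three in the first group, so the omission follows the objectives. For BUP, AUC0-28days and Cmax are primary, while AUClast, Tmax and Ctrough share one exploratory objective. Modelling only AUClast of these three is a choice. It contradicts no stated rule.

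**2. Is late exposure otherwise unseen?** Table 3 schedules PK samples on Days 15, 18, 22, 25 and 29. Section 9.3.1 summarises each scheduled time point by location and plots mean curves. A late divergence would be visible over five visits, though without a between-site interval.

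**3. What must happen for AUC0-28days to hide a late loss?** The documents give no depot model, so one is assumed: C(t) = A·2^(−t/3) + B·2^(−t/T). The fast phase has a 3-day half-life and carries 0-30% of reference exposure. T is the slow half-life. The case with no fast phase can be checked by hand, with AUC0-28days = B·(1 − 2^(−28/T))·T/ln 2:

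| T (days) | 2^(−28/T) | AUC0-28days / B |
|---|---|---|
| 52 | 0.6885 | 23.37 |
| 30 | 0.5237 | 20.62 |
| 60 | 0.7236 | 23.93 |
| 43 | 0.6368 | 22.53 |

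*Faster release, equal total absorption.* The ratio of B is T(ref)/T(test).
- 52 vs 30 days: B ratio 52/30 = 1.733; AUC0-28days ratio 1.733 × 20.62/23.37 = 1.53.
- 60 vs 43 days: B ratio 60/43 = 1.395; AUC0-28days ratio 1.395 × 22.53/23.93 = 1.31.

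With a 30% early share these fall to 1.22 and 1.12. The AUC0-28days point estimate moves without any help from Ctrough.

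*Faster release plus lower absorption, forced to an AUC0-28days ratio of 1.00.*
- 52 vs 30 days: B ratio 23.37/20.62 = 1.133; Ctrough ratio 1.133 × 0.5237/0.6885 = 0.86; total AUC ratio 1.133 × 30/52 = 0.65.
- 60 vs 43 days: B ratio 23.93/22.53 = 1.062; Ctrough ratio 1.062 × 0.6368/0.7236 = 0.93; total AUC ratio 1.062 × 43/60 = 0.76.

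Across early shares of 0-30%, the Ctrough ratio stays at 0.86 and 0.93 to two decimals (0.935 at most in the second case). Total AUC ranges over 0.65-0.76 and 0.76-0.83. The 30-day slow phase lies outside the protocol's 43-60 days.

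**4. What would the added interval show?** Section 9.5 aims for at least 15 PK-evaluable participants per location. The documents give no CV, so 30-60% is assumed. The 90% CI factor is exp(t(0.95, 56) × s × √(2/15)), with s = √ln(1 + CV²), t = 1.673 and √(2/15) = 0.365.

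| CV | s | Factor | CI at 0.86 | CI at 0.934 |
|---|---|---|---|---|
| 30% | 0.294 | 1.196 | 0.72-1.03 | 0.78-1.12 |
| 60% | 0.555 | 1.403 | 0.61-1.21 | 0.67-1.31 |

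Every interval includes 1.00.

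**5. Would the change be one sentence?** Not quite. Section 9.3.1 sets values below the quantification limit to zero for summaries, and zero has no logarithm. The Day 29 column in Table 3 also serves as the early-termination visit, so an early sample could be mistaken for Ctrough. The PK Evaluable Analysis Set does not explicitly require a Day 29 sample. The ±1 day visit window is harmless: one day changes the concentration by a factor of 2^(−1/43) = 0.984 to 2^(−1/60) = 0.989.

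**The case for a change.** The best case for the addition is BUP. AUClast and Ctrough sit under the same objective, and the one that is modelled adds least to the primary endpoint. Summaries and mean curves do not give a ratio with an interval. With no hypothesis tested, six more descriptive ratios (three sites, two analytes) spend no alpha and need no new samples. Wide intervals are also a weak counter-argument in an estimation study, since the primary ratios come from the same number of participants.

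Much of this stands. The protocol does leave Ctrough out, and a BUP Ctrough ratio would be a reasonable descriptive table. What does not follow is that the plan is deficient. The rationale concerns depot release of BUP and gives no reason for a metabolite ratio. The protocol text cannot establish that the trial omits the analysis, because it defers detail to a main SAP that is not among the documents. The only SAP document available is an addendum on medication classification. It opens with "After database lock, it was noted that the appendix of the SAP", so the database was already locked, and an addition made now could not count as pre-specified.

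The related wish to limit conclusions to 28 days after one dose is largely met. The endpoint name carries the 28 days, Table 7 defines the area from Day 1 to Day 29, and the primary objective concerns bioavailability "following a single SC injection of SUBLOCADE in participants with OUD".

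**Conclusion.** The concern does not hold. No number, rule or analysis in the plan is wrong, and nothing the trial can conclude from its primary comparison depends on a modelled Ctrough. The omission matches the stated objectives for norbuprenorphine and is a defensible choice for an exploratory BUP parameter.

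The scenario that would make it matter needs faster release and lower absorption that cancel in AUC0-28days. Even then the Ctrough ratio would be 0.93 for slow half-lives at the ends of the protocol's range, or 0.86 for a slow phase shorter than that range. Neither would be separated from 1.00 at 15 per arm. These sizes rest on the assumed two-phase profile and on assumed CVs of 30-60%. For the 0.86 case the upper limit falls below 1.00 only if s is under ln(1/0.86)/(1.673 × 0.365) = 0.247, a CV of about 25%.

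A post hoc BUP Ctrough ratio, labelled as such, is a matter of preference. Whether the main SAP already planned one cannot be determined from these documents.

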9.3.5 Other Safety Analyses

TEAEs are defined as AEs with a start time that is equal to or later than the initiation of the drug treatment or any AE already present that worsens in either severity or frequency following drug exposure. Specifically, TEAEs following exposure to SUBOXONE treatment will be associated with the Run-in Period and those following SUBLOCADE treatment will be associated with the Post-randomisation Period.

TEAEs will be summarised separately for the Post-randomisation Period and the Run-in Period using safety analysis set and run-in safety analysis set, respectively. The summaries will be by injection site and overall for the Post-randomisation Period, and overall only for the Run-in Period. Complete details of the safety analyses will be provided in the SAP.

Adverse events will be coded using MedDRA and grouped by system organ class. Incidence and incidence proportion of TEAE (number and percentage of participants reporting the TEAE at least once during the Post-randomisation Period and the Run-in Period, as applicable) will be summarised by system organ class and preferred term. Separate summaries will be provided for all TEAEs, TEAEs identified as injection site reactions, serious TEAEs, drug related TEAEs, and TEAEs leading to discontinuation of study treatment.

9.4 Interim Analysis

No interim analysis is planned.

9.5 Sample Size Determination

No formal statistical power analysis was performed to determine the sample size of this study. Based on historical experience from previous similar clinical trials, approximately 80 randomised participants was considered adequate to achieve at least 15 PK evaluable

Confidential 48 of 64

participants per injection site location to assess the relative bioavailability of SUBLOCADE 300 mg at each of the alternate injection site locations compared to the abdomen (the reference injection location).

Confidential 49 of 64

10 SUPPORTING DOCUMENTATION AND OPERATIONAL CONSIDERATIONS

10.1 Appendix 1: Regulatory, Ethical, and Study Oversight Considerations

10.1.1 Regulatory and Ethical Considerations

- This study will be conducted in accordance with the protocol and with the following:
 - Consensus ethical principles derived from international guidelines including the Declaration of Helsinki and Council for International Organizations of Medical Sciences (CIOMS) international ethical guidelines
 - Applicable ICH GCP guidelines
 - Applicable laws and regulations
- The protocol, protocol amendments, ICF, investigator's brochure, and other relevant documents (eg, advertisements) must be submitted to an IRB/IEC by the investigator and reviewed and approved by the IRB/IEC before use in the study. If required by local regulations, the protocol should be re-approved by the IRB/IEC annually. The IRB/IEC must be constituted and operate in accordance with the principles and requirements of ICH/GCP.
- Any amendments to the protocol will require IRB/IEC approval before implementation of changes made to the study design, except for changes necessary to eliminate an immediate hazard to study participants.
- Protocols and any substantial amendments to the protocol may require health authority approval prior to initiation except for changes necessary to eliminate an immediate hazard to study participants.
- The investigator will be responsible for the following, as applicable:
 - Providing written summaries of the status of the study to the IRB/IEC annually or more frequently in accordance with the requirements, policies, and procedures established by the IRB/IEC
 - Notifying the IRB/IEC of SAEs or other significant safety findings as required by IRB/IEC procedures
 - Providing oversight of the conduct of the study at the site and adherence to requirements of 21 CFR, ICH guidelines, the IRB/IEC, European regulation 536/2014 for clinical studies, European Medical Device Regulation 2017/745 for clinical device research, and all other applicable local regulations

10.1.2 Financial Disclosure

Investigators and sub-investigators will provide the sponsor with sufficient, accurate financial information as requested to allow the sponsor to submit complete and accurate financial certification or disclosure statements to the appropriate regulatory authorities. Investigators are responsible for providing information on financial interests during the course of the study and for 1 year after completion of the study.

Confidential 50 of 64

10.1.3 Informed Consent Process

- The investigator or the investigator's representative will explain the nature of the study to the participant and answer all questions regarding the study. Potential participants must be informed that their participation is voluntary. They will be required to sign a statement of informed consent that meets the requirements of 21 CFR 50, local regulations, ICH guidelines, and privacy and data protection requirements, where applicable, and the IRB/IEC or study centre.
- Written informed consent must be obtained prior to any study-related procedures.
- The authorised person obtaining the informed consent must also sign the ICF.
- Participants must be re-consented to the most current version of the ICF(s) during their participation in the study, if required by the IRB/IEC.
- A copy of the ICF(s) must be provided to the participant.
- Any changes to the ICF must be reviewed and approved by Indivior before submission to the IRB/IEC.
- In the event that new safety information emerges that represents a significant change in the risk/benefit assessment, the ICF will be updated accordingly and submitted to the IRB/IEC for approval.

Participants who are rescreened are required to sign a new ICF.

10.1.4 Data Protection

- Participants will be assigned a unique identifier by the sponsor. Any participant records or datasets that are transferred to the sponsor will contain the identifier only; participant names or any information which would make the participant identifiable will not be transferred.
- Participants must be informed that their personal study-related data will be used by the sponsor in accordance with local data protection law. The level of disclosure must also be explained to the participant who will be required to give consent for their data to be used as described in the informed consent.
- Participants must be informed that their study records may be examined by Clinical Quality
 Assurance auditors or other authorised personnel appointed by the sponsor, by the IRB/IEC,
 and by inspectors from regulatory authorities.
- All participant bodily fluids and/or other materials collected shall be used solely in accordance with the study protocol and the ICF signed by the participant, unless the participant agrees to additional procedures in writing with the sponsor.
- The investigator must maintain all study-related records (except for those required by local regulation to be maintained elsewhere) in a safe and secure location throughout the conduct and following the closure of the study. The records must be accessible upon request (eg, for an IRB/IEC, Indivior, or regulatory inspection) along with the facility, study personnel, and supporting systems/hardware. All documents pertaining to the study, including all versions of the approved study protocol, copy of the ICF and other documents as required per local laws and regulations (eg, Health Insurance Portability and Accountability Act documents), completed CRFs, source records (participant records,

Confidential 51 of 64

participant diaries, hospital records, laboratory records, drug accountability records, etc), and other study-related materials will be retained in the permanent archives of the study site.

Where permitted by local laws and regulations, records may be maintained in a format other than hard copy (eg, electronically in an electronic medical records system). The investigator must ensure that all reproductions are an accurate legible copy of the original and that they meet necessary accessibility and retrieval standards. The investigator must also ensure that a quality control process is in place for making reproductions and that the process has an acceptable backup of any reproductions.

The minimum retention time for retaining study records will be in accordance with the strictest standard applicable for the study site as determined by local laws, regulations, or institutional requirements. At a minimum, records will be maintained as dictated by ICH/GCP guidelines, as well as in accordance with the site's SOP requirements. If the investigator withdraws from the study (eg, relocation, retirement) all study-related records should be transferred, in a written agreement with Indivior, to a mutually agreed upon designee within Indivior-specified time frame.

- The contract between sponsor and study sites specifies responsibilities of the parties related data protection, including handling of data security breaches and respective communication and cooperation of the parties.
- Information technology systems used to collect, process, and store study-related data are secured by technical and organisational security measures designed to protect such data against accidental or unlawful loss, alteration, or unauthorised disclosure or access.

